4. INVESTIGATIONAL PLAN

4.1. Summary of Trial Design

Methodology

DESCRIPTION

This is a 3-year (maximum), single-arm, open-label, multicenter, phase 3 follow-on trial of ARGX-113-1704 to evaluate the long-term safety and tolerability of efgartigimod in patients with gMG. The trial consists of 2 parts: Part A (1 year) and Part B (up to maximum 2 years or until efgartigimod becomes commercially available or another option to access efgartigimod is available, whichever option comes first. The additional part (Part B) was added to ARGX-113-1705 in order to provide the patients with the chance to have access to efgartigimod while it is not yet commercially available or available through another patient program. This extension will also enable additional long-term safety and tolerability data to be collected.

A variable number of treatment periods consisting of 4 weekly infusions of efgartigimod (10 mg/kg of body weight) infused over a period of 3 weeks will be administered to eligible patients on an “as needed basis” on top of their SoC. The time between treatment periods is based on the duration of the treatment effect and may vary from patient to patient and within each patient from period to period (patient-tailored approach).

The first visit of trial ARGX-113-1705 will coincide with the last visit of trial ARGX-113-1704 for each patient.

The SEB will be set at the first trial visit, while the baseline of each subsequent treatment period (TP_nB for Part A or TPE_nB for Part B) will be set at visit 1 of each corresponding treatment period.

ROLL-OVER

At the EoS visit of trial ARGX-113-1704, eligible patients will be offered the option to roll over into this trial. Patients in need of (re-)treatment in trial ARGX-113-1704 but who cannot complete a Treatment Cycle within the time frame of that trial, may immediately roll over to this trial to receive treatment with efgartigimod.

Patients who discontinued early from trial ARGX-113-1704 or discontinued early from randomized treatment for rescue or pregnancy reasons or for an SAE that is likely to result in a life-threatening situation or pose a serious safety risk in that trial will not be offered the option to roll over into this trial.

Patients who discontinued early from randomized treatment for other reasons and patients who had a temporary interruption from randomized treatment in trial ARGX-113-1704 may be offered the option to roll over into this trial.

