Patients who have completed at least 1 cycle of treatment and at least 1 year of trial ARGX-113-1705 and have started Part B are eligible to enroll in the open-label trial ARGX-113-2002 to receive efgartigimod by SC administration.

Before enrolling in ARGX-113-2002 from Part B, patients must first complete the early discontinuation (ED) visit assessments specified in [Table 2](#). The previous efgartigimod IV dose must have been received at least 30 days before entry into ARGX-113-2002.

Patients can enroll in ARGX-113-2002 until recruitment for this study is closed. Patients who enroll in ARGX-113-2002 will not return to ARGX-113-1705.

(RE-)TREATMENT (Part A)

Each patient will start a (new) treatment period with efgartigimod when all of the following criteria are met:

- The patient has completed the previous treatment period (ie, after visit 4)
- The patient has a total MG-ADL score of ≥ 5 points with more than 50% of the total score due to non-ocular symptoms
- The patient has a reduction in the total MG-ADL score of < 2 points compared to the score at:
 1. The last treatment cycle baseline (TCB) in trial ARGX-113-1704 for the first treatment period (TP₁) in trial ARGX-113-1705
 2. The last treatment period Baseline (TP_nB) for all subsequent treatment periods (TP_{n+1}) in trial ARGX-113-1705

However, patients may not receive (re-)treatment with efgartigimod if, at the time of (re-)treatment, they have clinical evidence of bacterial, viral or fungal disease, or any other significant disease which could confound the results of the trial or put patients at undue risk. Patients who require an additional treatment but who are not eligible to receive (re-)treatment for the reasons listed here will remain in the trial to receive appropriate alternative MG treatment (see [Appendix 5](#) and [Appendix 6](#)).

Patients who have a treatment failure to efgartigimod for 3 consecutive treatment periods will be discontinued from the trial. Treatment failure means the absence of a decrease of at least 2 points in total MG-ADL score compared to the corresponding TP_nB in at least 50% of the assessments (ie, TP_nV2, TP_nV3, TP_nV4, and the first posttreatment period visit).

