If a patient becomes eligible for (re-)treatment with efgartigimod by meeting the criteria for the total MG-ADL score as stated in [Section 4.1](#), but cannot complete the entire treatment period during Part A (ie, after day 336) then the patient can be transitioned to Part B after completing the end of Part A (EoA) visit assessments ([Table 1](#)). These assessments should be completed even if the patient is unwilling or unable to continue to Part B.

The transition to Part B can be either at ITPE₀V_n or TPE₁V₁, depending on the patient status regarding the need for (re-)treatment upon transition from Part A. The first visit in Part B will always coincide with the EoA visit in Part A. The assessments done for the last visit in Part A should not be repeated in Part B.

(RE-)TREATMENT (Part B)

If the patient feels that his/her condition has deteriorated, then the investigator may start a new treatment period at an intertreatment period (ITPE) visit or the patient may contact the investigator to attend an unscheduled visit.

A patient can start the next treatment period and receive efgartigimod if all of the following criteria are met:

- The patient has completed the previous treatment period (ie, after visit 4)*
- The investigator determines that the patient will benefit from re-treatment
- There is at least 1 calendar month (minimum 4 weeks) between treatment periods (ie, between TPE_nV4 and TPE_{n+1}V1)

*A patient who has had a temporary interruption of trial treatment in Part A may also continue into Part B of the trial and receive (re-)treatment if the conditions in Section 4.4.1 are met.

However, patients may not receive (re-)treatment with efgartigimod if, at the time of (re-)treatment, they have clinical evidence of bacterial, viral or fungal disease, or any other significant disease which could confound the results of the trial or put patients at undue risk.

If a patient becomes eligible for (re-)treatment with efgartigimod but cannot complete the entire treatment period within the duration of the trial, the patient should continue to the EoS visit.

If the investigator considers that the patient will not have a clinical benefit from (re-)treatment then the patient cannot start a new treatment period. The patient should then continue to the EoS visit.

STANDARD OF CARE (SoC)

In Part A:

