4.4. Early Discontinuation

The criteria for roll-over into this trial (see Section 4.3) are to be followed explicitly. If it is noted that a patient who does not meet 1 or more of the inclusion and/or meets 1 or more of the

exclusion criteria is inadvertently rolled over, the Medical Monitor at sponsor's designated CRO and the sponsor's Medical Director must be contacted immediately.

Early discontinuation from the trial is defined as the permanent cessation of further participation in the trial prior to its planned completion.

Patients **must** be discontinued early from the trial if:

- They withdraw their consent.
- The investigator, after discussion with the sponsor's Medical Director, deems it is in the patient's best interest.
- Patient is pregnant.
- Patient receives rescue therapy (Part A only).
- Patient develops an SAE that is likely to result in a life-threatening situation or pose a serious safety risk to the patient.
- Prohibited medication is taken (Part A only) (see Section 6.8.1).

Patients **might** discontinue early from the trial if:

- Patient has clinical evidence of bacterial, viral or fungal disease or any other significant disease which could confound the results of the trial or put the patient at undue risk. In this situation, decision on whether or not to discontinue patients early from trial will depend on the evaluation on a case-by-case basis. Patients who, after evaluation of the above situations are not discontinued from the trial, may have a temporary interruption from trial treatment (see Section 4.4.1).

For patients who discontinue early from trial, the assessments will depend on the visit at which it was decided that the patient had to discontinue (see Section 5.4, Figure 1, and Figure 2).

Patients who discontinue early from the trial within a treatment period should perform the planned assessments of the corresponding treatment period visit. These patients will not receive any further administration of efgartigimod during the trial and will return for the ED visit 1 month (30 ± 2 days) after the last dose administration. An unscheduled visit can be organized if deemed necessary by the investigator.

Patients who discontinue early from the trial between the last visit of a treatment period (TP_nV4 or TPE_nV4) and the next intertreatment period visit (ITP_nVn or $ITPE_nVn$) should perform the ED assessments 1 month (30 ± 2 days) after the last dose administration.

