8. STATISTICS

The statistical analyses will be performed by sponsor's designated CRO using statistical analysis systems SAS® (SAS Institute, Cary, NC, United States [US]) version 9.2 or higher, and the software package R, if applicable. The standard operating procedures (SOPs) and work instructions of sponsor's designated CRO will be used as the default methodology if not otherwise specified.

Any change to the data analysis methods described underneath will be mentioned in the statistical analysis plan (SAP). Any additional analysis, and the justification for making the change, will be described in the Clinical Trial Report (CTR). Additional exploratory analyses of the data will be conducted as deemed appropriate.

Due to the single-arm, open-label nature of the design, evaluation of all endpoints will be essentially descriptive. Endpoints will be summarized by treatment (as received in ARGX-113-1704).

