1.3 EXPECTED SAMPLE SIZE

The maximum number of patients in ARGX-113-1705 is the number of patients who participated in trial ARGX-113-1704 which is 167.

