2.2 PHASES, PERIODS AND TIME POINTS

2.2.1 *Phases and periods*

All events and assessments will be allocated to phases and periods (see Table 1). A patient can start in 1705 in an inter-treatment period or in a cycle, depending on the patient status regarding the need for (re-)treatment upon roll-over. Each period following ITPO coincides with a cycle and includes the 4 administrations of efgartigimod and the inter-treatment period (ITP) visits. The length of the ITP is patient specific and can differ between the different periods. The number of patients may decline for each subsequent cycle.

	Statistical Analysis Plan	
ARGX-113-1705	Final Analysis	Final 1.0 of 20SEP2022

Table 1: phase/period definition

Phase	Period	Start	End
Treatment	ITP0	Earliest of (date of signing the informed consent form (ICF) and date of roll-over), with 00:00 added as time part.	First administration date/time in cycle 1 – 1 minute
	Cycle 1	First administration date/time in cycle 1	First administration date/time in next cycle – 1 minute or if last cycle: date of last contact, with 23:59 added as time part
	Cycle n	First administration date/time in cycle n	First administration date/time in next cycle – 1 minute or if last cycle: date of last contact, with 23:59 added as time part
	Cycle x	First administration date/time in cycle x	Date of last contact, with 23:59 added as time part

AEs and concomitant medications will be allocated to phases and periods as described in sections 5.1.2 and 3.5.2 respectively. All other assessments will be allocated to phases and periods based on the assessment date/time.

In case of (partially) missing date/time fields disabling allocation or date(time) equal to dosing date(time), information from visit label and protocol schedule of assessments (SoA) will be used to allocate to the correct period. If this is not possible, assessments will be allocated to the first possible cycle (not ITP0) unless the available parts of the assessments start or stop date/time provide evidence the assessments did not occur during that period.

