4. EFFICACY, PHARMACODYNAMICS AND ANTI-DRUG ANTIBODIES ANALYSES

4.1 EFFICACY

4.1.1 *Available data*

Efficacy will be assessed using MG-ADL (part A and B) and QMG (part A only).

4.1.2 *Endpoints and derivation rules*

1) Actual values and change from baseline and CnB in total MG-ADL score will be analysed descriptively and categorically.

Categories to be used for actual values in MG-ADL total score: 0, 1, 2, 3, 4, 5-7, 8-9, 10-12, 13-16, 17-20 and 21-24.

Categories to be used for changes from baseline and CnB in MG-ADL total score: >0, 0, -1, -2, -3, -4, -5, -6, -7, -8, -9, -10, <-10. Number of patients, percentages and cumulative percentages will be shown.

In addition to the planned timepoints, following timepoints will be shown for each cycle:

- Maximum drop from baseline and CnB in MG-ADL
- Minimum MG-ADL score: descriptively and categorically

Missing data will not be considered.

Analysis will be done on AChR-Ab seropositive patients, AChR-Ab seronegative patients and overall.

2) Actual values and change from baseline and CnB in total QMG score will be described descriptively and categorically as for the MG-ADL score. For the categorization of the QMG total score actual values a category of >24 will be added.

4.1.3 *Statistical analysis*

Summary statistics will be provided in terms of absolute values and changes from baseline (overall) and CnB (for each cycle) for MG-ADL and QMG total scores in AChR-Ab seropositive patients, AChR-Ab seronegative patients and the overall safety population.

Absolute values and changes from baseline (overall) and CnB (for each cycle) in MG-ADL and QMG total scores will also be categorized, including the number of patients within each category, the percentage, and the cumulative percentage.

See section 8 for a list of tables and listings.

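### By-cycle tables mix change within patients with change in who is present, so trends across cycle columns cannot be read as maintained or lost effect without same-patient tables

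*SAP*

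**What the plan says.** - **Dosing is as needed.** Protocol 4.1: "The time between treatment periods is based on the duration of the treatment effect". In Part A a new course needs an MG-ADL total of at least 5 and less than 2 points of remaining benefit against the last treatment baseline.
- **Exits in Part A.** Protocol 4.1, under Part A re-treatment: "Patients who have a treatment failure to efgartigimod for 3 consecutive treatment periods will be discontinued from the trial". Protocol 4.4 also makes rescue therapy a mandatory exit, in Part A only.
- **Entry to a new course in Part B.** One condition in Protocol 4.1 is: "The investigator determines that the patient will benefit from re-treatment".
- **Tables.** Displays are by treatment and cycle (SAP 2.4.3), without imputation (SAP 2.3.1). Event-type safety percentages use a denominator per treatment and cycle, and by-visit tables keep any visit with at least 10 patients (SAP 2.4.1). MG-ADL, QMG and PD are summarised as values and as changes from first-cycle and cycle baseline (SAP 4.1.3, 4.2.3). AEs are tabulated by cycle and overall (SAP 5.1.3).
- **Acknowledgement.** SAP 2.2.1: "The number of patients may decline for each subsequent cycle". It gives no reason for the decline and no way of reading across it.
- **Related displays.** SAP 3.1 tabulates cycle duration, and discontinuation reasons by cycle. The table list in SAP 8.1 contains no fixed-cohort or paired-across-cycles display.

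**The concern.** Protocol 4.2 says the safety endpoints are to be evaluated by cycle as well as over the whole trial, and a reader of a repeat-course trial will naturally look along the cycle columns. If patients with poor response leave while patients with short intervals accumulate cycles, the late columns hold a selected group. A level row of MG-ADL means could then be a maintained effect, or a loss offset by selection. A falling AE percentage could be better tolerability, or just shorter cycles. The planned tables cannot tell these apart. What is at stake is any statement that effect or tolerability is consistent over repeated courses.

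**Working it through.** The plan has no figure to reproduce: Protocol 8.1 gives no sample-size calculation, and SAP 1.3 gives only a ceiling of 167 patients.

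**1. Who can reach a high cycle (document inputs only)**

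Visit 4 falls 21 days after visit 1, and the first Part A intertreatment visit 30 days later, so the shortest interval at scheduled visits is 51 days. The last Part A start is day 336. The trial ends by day 1095, so the last start is day 1095 − 21 = 1074. With a first start on day 1 and interval g, the number of starts by day D is 1 + floor((D − 1)/g).

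- g = 51: 1 + floor(335/51) = 7 by day 336; 1 + floor(1073/51) = 22 by day 1074.
- g = 21 + 6 × 30 = 201: 2 by day 336; 6 by day 1074.
- Starting cycle 10 by day 1074 needs a mean interval of at most 1073/9 = 119 days.

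Cycle 10 therefore cannot include patients with long-lasting benefit. This needs no assumption about effect size.

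**2. What a difference between two columns contains**

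Let M_k be the cycle k mean over the patients who started cycle k. Then

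M_k − M_1 = [mean within-patient change, in those in cycle k] + [cycle 1 mean of those patients − cycle 1 mean of all].

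The SAP tables show only the sum. The first illustration uses assumed inputs, none from the documents except the ceiling of 167, the three-year limit and the three-failure stop: mean cycle change −4.5 points, between-patient SD 2, within-patient SD 1.5, median gap 60 days (log-SD 0.6), failure scored as a change worse than −2. A positive difference is a loss of benefit. The stop is applied in both parts; confining it to Part A leaves more of the loss visible in the second row and hardly alters the first.

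| Assumed scenario | M_1 | M_10 | Cycle 1 mean of those in cycle 10 | Shown | Within patient | Composition |
|---|---|---|---|---|---|---|
| Loss 0.1 per cycle, 30% of failures leave at once | −4.51 | −4.51 | −5.42 | 0.00 | +0.91 | −0.91 |
| Loss 0.1 per cycle, three-failure stop only | −4.49 | −4.07 | −4.96 | +0.42 | +0.89 | −0.47 |
| No loss, 30% leave, deeper responders relapse later | −4.50 | −4.94 | −4.95 | −0.44 | +0.01 | −0.45 |
| No loss, 30% leave, deeper responders relapse sooner | −4.49 | −5.40 | −5.40 | −0.91 | 0.00 | −0.91 |

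As a control, with identical patients and no response-based exit, a loss of 0.1 per cycle is fully visible: −4.50 to −3.61.

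The second illustration assumes a mean drop of 5 points, between-patient SD 2.2, visit SD 1.5, the three-failure stop, and 5% leaving after a response against 20% after a non-response. A true loss of 0.1 × 9 = 0.9 by cycle 10 shows as 0.17 to 0.28, according to how failure and exit are coded. It shows as 0.54 when random drop-out does not depend on response. The paired same-patient difference gives 0.91 to 0.93, and about 0.01 in size when there is no loss.

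**3. Direction**

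With the second set of inputs, no loss, a three-year calendar and the failure stop in Part A only, the cycle 10 mean drop is 5.54 if depth and duration of response are uncorrelated and 5.23 at correlation 0.5. With an equal 5% exit the figures are 5.27 and 4.96. Cycle 1 is 5.00 throughout. The spurious trend thus runs from about +0.5 to about zero.

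**4. AE percentages and cycle length**

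With a constant hazard λ, the chance of at least one AE in a cycle of L days is 1 − exp(−λL/365.25). With λ = 2 per year (assumed), L = 51 gives 24% and L = 201 gives 67%. In the first illustration the percentage with an AE falls from 37% in cycle 1 (median length 72 days) to 30% in cycle 12 (64 days) under an unchanged hazard. SAP 5.1.2 defines follow-up for event rates as the whole treatment phase, so no within-cycle person-time is defined.

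**The case against.** The strongest reply is that the trial makes no inference across cycles. Protocol 8 states: "Due to the single-arm, open-label nature of the design, evaluation of all endpoints will be essentially descriptive". The primary and secondary endpoints are safety over the duration of the trial; MG-ADL, QMG and PD are tertiary. AEs are also tabulated overall, with patient-year rates. Cycle duration and discontinuation reasons by cycle let a reader see who is leaving, and changes from baseline use each patient's own value. The simulated sizes rest on inputs that the documents do not give.

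Much of this stands, and it limits the point. Three stronger readings are tempting and not supported:

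- **That selection alone produces a steady row.** With a constant effect in every patient, the illustrations give an apparent improvement, or roughly none where depth and duration of response offset each other. A level row that misleads needs a real loss and an opposing selection.
- **That poor responders are removed throughout.** The three-failure and rescue exits belong to Part A. Three consecutive failures cannot remove anyone before cycle 4, and Part B allows the treatments that count as rescue in Part A.
- **That the primary safety result is biased, or that AE rates fall because susceptible patients leave.** Overall incidence does not compare cycles, and nothing in the documents quantifies loss of susceptible patients. The demonstrable AE problem is cycle length.

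What does not stand is that descriptive status disposes of the matter. A description by cycle still invites comparison of its columns. A change from a patient's own baseline is still averaged over whoever is left, and discontinuation tables do not show how far the means have moved.

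**Conclusion.** The point holds as a limit on interpretation. By-cycle MG-ADL, QMG, IgG and AE summaries are computed on whoever started each cycle, and starting a late cycle depends on response and its duration. Neither a trend nor its absence across columns shows what happened within patients.

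The mechanism comes from the documents; its size and direction do not. Under the assumptions above, a true 0.9-point loss by cycle 10 appears as about 0.2 to 0.5 and can vanish, and with no loss there can be an apparent improvement. These figures show what is possible and do not forecast this trial. Overall AE incidence, and so the primary and secondary endpoints, is not affected. The change is worth making because it is cheap and separates the two components, but the main safety conclusion does not depend on it.

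**What to change.** Add fixed-cohort tables that show cycles 1 to k only in patients who started at least k cycles, with the cycle baseline and the paired within-patient difference from cycle 1:

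- **MG-ADL:** k = 3, 5 and 7, and higher while at least 20 patients qualify.
- **QMG and total IgG:** k = 3, and k = 5 only if at least 20 patients have Part A data for all five cycles. Both are collected in Part A only, and Protocol 7.2.2 takes six treatment periods as the Part A maximum. A seventh start by day 336 would need re-treatment at the first intertreatment visit every time, so larger k is not useful.
- **AE overview by cycle:** event rates on person-time within each cycle, plus fixed-cohort versions for k = 3 and k = 5.

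State in the SAP that by-cycle columns are not within-patient trends, and that maintenance across cycles is read from the fixed-cohort tables.

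The cost is a few repeat tables from existing datasets, with no new data and no change to trial conduct. The downside is smaller numbers, and results that apply only to patients who reach k cycles.
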